7.7.4 Collection of EORTC QLQ-C30 and Bowel Diary

Paper Quality of Life (QoL) instruments will be administered pre-dose on C1D1.

The EORTC QLQ-C30 and a bowel diary (for MTC patients only) will be used (refer to [Appendix J](#)) and should be implemented for newly enrolled patients. Only patients who have completed the questionnaire at baseline should complete subsequent questionnaires at the specified follow-up periods.

For EORTC QLQ-C30, subsequent assessments will occur at the same cycle visits as disease assessments until EOT. Each assessment should be performed before the subject learns the results of his or her restaging.

For MTC patients, the bowel diary assessments will be collected weekly on Cycle 1, and on Day 1 of every cycle thereafter through EOT. Inaccurate recording will not be considered a protocol violation.

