6.10.2. Bowel Diaries

The bowel diary questionnaire is a modified version of the STIDAT (Systemic Therapy Induced Diarrhea Assessment Tool), a standardized patient-reported questionnaire used to assess systemic therapy-induced diarrhea in oncology patients (Lui et al. 2017). The questionnaire used in this study contains 11 questions and assesses the patient's perception of having diarrhea, daily number of bowel movements, daily number of diarrhea episodes, the presence of urgency, presence of abdominal discomfort, fecal incontinence, patient's perception of diarrhea severity, and QoL. In the case of missing items in the QoL subscale, the scale will be excluded from the analysis and no imputation will be made.

This questionnaire uses a weighted scoring system, which will not be applied in this study due to the modification of the tool used in this study that invalidates the weights and could produce incorrect findings.

The mean/SD and median/range total QoL score, mean (SD) number of bowel movements (item 3), mean (SD) number of diarrheal episodes (item 2), and number/proportion of patients experiencing diarrhea (item 1), categorical response to severity of diarrhea (item 1 for those with diarrhea), urgency (item 4), abdominal discomfort (item 5), and fecal incontinence (item 6), respectively, will be summarized descriptively at each time point at which the data were collected for all patients, and separately for those who had diarrhea at baseline.

Item level mean/SD and median/range values will be reported for each QoL scale (items 8-12) at each study visit. Additionally, mean scores across time will be presented in a line plot for items 8-12. Change of score from baseline will also be summarized for each scale at each visit, and be presented in a line plot.

Worsening on the bowel diary is defined as any stepwise categorical decline in the diarrhea item 1 (such as, no diarrhea to minimal, moderate or severe; minimal to moderate or severe; moderate to severe), and improvement is defined as any stepwise improvement (such as minimal to no diarrhea, moderate to minimal or no diarrhea, severe to moderate, minimal or no diarrhea).

For all change-from-baseline measures, the analysis set will include all treated patients who have baseline and at least one post-baseline PRO assessment on the item being evaluated.

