The number and proportion of patients experiencing worsening or improvement from baseline will be reported at each study visit at which the bowel diary is collected. Kaplan-Meier method will be used to evaluate time to first improvement (among the baseline diarrhea population) and time to first worsening (for the entire Cohort 2), respectively. For patients in the baseline diarrhea population, those who didn't experience any improvement or worsening will be censored at the date of their last bowel diary assessment. For patients in Cohort 2 who didn't have diarrhea at baseline, time to first worsening will be censored at the date of data cutoff.

For patients with improvement, the duration of improvement (defined as time from first improvement to the return to or below the baseline categorical level) will be reported as median, range, mean/SD days. Similarly, the duration of worsening (defined as time from first worsening to the return to or above the baseline categorical level) will be reported as median, range, mean/SD days.

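### SAP 6.10.2 summarises the bowel-diary durations of improvement and worsening without censoring ongoing episodes, so the figures tend to be biased short, possibly severely if improvement lasts

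*SAP*

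**What the plan says.** SAP 6.10.2 starts each duration at the first change in diarrhea category and ends it when the patient returns to the baseline category. On the favorable side it states: "the duration of improvement (defined as time from first improvement to the return to or below the baseline categorical level) will be reported as median". Alongside the median it asks for the range, the mean and the SD, in days. For worsening, "the duration of worsening (defined as time from first worsening to the return to or above the baseline categorical level) will be reported as median" with the same companions. Neither sentence says what to do when the return has not happened.

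The same section does use survival methods, but for onset only: "Kaplan-Meier method will be used to evaluate time to first improvement (among the baseline diarrhea population) and time to first worsening". Its censoring rule matches that scope. Of patients who had diarrhea at the start, it says: "those who didn't experience any improvement or worsening will be censored at the date of their last bowel diary assessment". That covers patients who never changed, not patients who changed and have stayed changed.

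Protocol 7.7.4 sets the diary weekly in Cycle 1 and then "on Day 1 of every cycle thereafter through EOT". Observation of an episode therefore stops when treatment stops. SAP 6.3 rules out imputation except for dates and leaves date rules to the relevant section; 6.10.2 contains none. By contrast, SAP 6.9.5 gives tumor duration of response, which is also an onset-to-loss time, a censoring table and a Kaplan-Meier summary.

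**The concern.** A duration that ends at return to baseline is a time-to-event variable. Some patients will still be improved when their diary ends, and they are the ones with the longest relief. A plain median or mean cannot use them properly. If they are left out, the summary describes only patients who lost their improvement within follow-up. If they are given the last diary date as an end, their durations are understated. Both errors go the same way.

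For improvement, a short figure understates how long relief lasts. For worsening, it would make deterioration look briefer than it was, to the extent that worsening episodes outlast follow-up. One SAP sentence can also yield two different answers depending on the programmer, with no rule for choosing between them.

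**Working it through.** The documents state no figure for either duration, so there is nothing to reproduce. The check has two parts.

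1. Does any rule supply an end date for an ongoing episode? The Kaplan-Meier and censoring sentences in SAP 6.10.2 concern first change only. SAP 6.3 defers to a date rule that 6.10.2 does not contain. Protocol 7.7.4 ends diary collection at end of treatment. No rule was found.

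2. How large could the effect be?

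Assumptions (not from the documents): true duration T is exponential with median m months, so λ = ln 2 / m; follow-up after first change, C, is independent and uniform over 3 to 18 months. For context, SAP 6.14 requires two post-baseline tumor assessments before the primary analysis, early discontinuations excepted. On the 8-weekly schedule that is about 16 weeks, or 16 × 7 / 30.4375 = 3.7 months from first dose, so a lower limit of 3 months after the change is not extreme.

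Formulas:
- Share of episodes with an observed end: p = 1 − (e^(−3λ) − e^(−18λ)) / (15λ).
- Median if only ended episodes count: the t solving G(t) = p/2, where G(t) = 1 − e^(−λt) up to 3 months and, beyond that, G(t) = 1 − e^(−3λ) + ∫ from 3 to t of λe^(−λs)(18 − s)/15 ds.
- Median if the last diary is the end date: the t solving e^(−λt) × P(C > t) = 0.5, with P(C > t) = 1 up to 3 months and (18 − t)/15 after.

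For m = 12, λ = 0.05776:
- p = 1 − (0.8409 − 0.3536)/0.8664 = 0.4375, so about 44% have an observed end.
- p/2 = 0.2188 and G(4.33) = 0.2186, so the ended-only median is about 4.3 months. The ended-only mean is 5.2, against a true mean of 1/λ = 17.3.
- At t = 6.86, 0.6728 × 0.7427 = 0.4997, so the last-diary median is about 6.9 months. The corresponding mean is p/λ = 0.4375 × 17.3 = 7.6.

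Same formulas, other true medians:

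| True median (months) | Share ended | Ended-only median | Last-diary median |
|---|---|---|---|
| 0.5 | 99.9% | 0.50 | 0.50 |
| 1 | 98.8% | 0.98 | 1.0 |
| 3 | 86% | 2.4 | 3.0 |
| 6 | 66% | 3.5 | 4.9 |
| 12 | 44% | 4.3 | 6.9 |
| 24 | 26% | 4.9 | 8.4 |

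A simulation with diaries every 28 days (200,000 patients per scenario) gives the same picture and shows what Kaplan-Meier does. The discrete diary dates move a true median of 1, 6 or 12 months to 1.8, 6.4 or 12.9.

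| Follow-up (months) | True median | Ended-only | Last diary as end | Kaplan-Meier |
|---|---|---|---|---|
| 3–12 | 1 | 1.8 | 1.8 | 1.8 |
| 3–12 | 6 | 2.8 | 4.6 | 6.4 |
| 3–12 | 12 | 3.7 | 5.5 | not reached |
| 12–24 | 12 | 7.4 | 12.0 | 12.9 |

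Kaplan-Meier recovers the diary-grid median wherever follow-up reaches it, and otherwise says that it was not reached. With 10 improvers, a true median of 12 months and follow-up of 3 to 12 months, about 3.3 would have an observed end.

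**The case against.** The strongest reply is that the SAP does not exclude anyone. It writes "For patients with improvement, the duration of improvement", which takes in every improver, and is merely silent on ongoing episodes; a programmer could close them at the last diary. That is fair. A reader might infer that only ended episodes will be counted. That is the literal consequence of the definition, but it is not the only possible handling. Cutting off at the last diary is less biased, and its median is even correct when the true median lies within everyone's follow-up (true median 6 months, follow-up 6 to 24 months: 6.0). It does not rescue the plan, because the mean is still short and the median is short whenever relief outlasts much of the follow-up.

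A reader might also conclude that the reported durations will be far too short. The documents do not support that without qualification. They give neither durations nor follow-up after a change, and the first table shows the bias vanishing for brief episodes. Worsening may well be brief, so a material bias in the drug's favor on that side is not shown.

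The section reports other things that bear on symptom relief: the proportions improved and worsened at each diary visit, and Kaplan-Meier time to first change. These stand as useful companions, but neither measures how long an improvement lasts.

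Finally, a reader might see an item-numbering error, since "The questionnaire used in this study contains 11 questions" while "Item level mean/SD and median/range values will be reported for each QoL scale (items 8-12) at each study visit". The section cites items 1 to 6 and 8 to 12, and 6 + 5 = 11. That fits a modified tool that skips item 7. Protocol Appendix J gives only references for the diary, so no error can be shown.

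**Conclusion.** The method as written is wrong for both durations: it applies uncensored summaries to times that will be incomplete for some patients. The direction is towards shorter durations, whether ongoing episodes are dropped or cut off at the last diary. The size depends on how long changes last relative to follow-up. It is negligible at a true median of about 1 month or less. At a true median of 12 months with follow-up uniform over 3 to 18 months, the reported median would be about 36% (4.3/12) or 57% (6.9/12) of the truth, depending on the handling. Those figures assume exponential durations and independent follow-up, neither of which the documents supply.

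The impact is limited. Protocol 9.1.3 lists the bowel diary as exploratory, and the analysis is descriptive. It concerns MTC patients with diarrhea at baseline, a subset of a cohort targeted at 20 or more. No conclusion on ORR depends on it.

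**What to change.** In SAP 6.10.2, replace the plain summaries of both durations with Kaplan-Meier estimates: median with 95% CI, and range with censored values marked. Censor any episode that has not returned to the baseline category at the date of the last bowel diary assessment, and state that this also applies at end of treatment, death and data cutoff. Report the number of episodes ended and the number ongoing. Because the diary stops with treatment, tabulate why observation ended for the censored patients, so that a reader can judge whether the censoring is likely to be informative.

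The cost is a few lines of SAP wording and a small programming change. Kaplan-Meier is already planned for this diary, the censoring date matches the one used for time to first change in the baseline diarrhea population, and SAP 6.9.5 offers a model in its treatment of tumor duration of response. No new data are needed.

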6.11. Safety Analyses

Safety analyses will be conducted on the safety population. Additionally, safety endpoints may be summarized by tumor type (NSCLC, TC, and MTC) pooled across cohorts.

6.11.1. Extent of Exposure

Exposure to selpercatinib will be summarized based on the following:

- Time on treatment
- Dose intensities
- Dosage modifications

6.11.1.1. Time on Treatment

Time on treatment (TOT) will be summarized descriptively. For patients who permanently discontinued selpercatinib as of the data cutoff date, TOT will be calculated as follows:

$$\text{TOT (weeks)} = (\text{Last Dose Date} - \text{First Dose Date} + 1)/7$$

The first and last dose dates reported on the "Exposure: First Dose" and "Exposure: Last Dose" case report form pages, respectively, will be used for the above calculation.

For patients continuing to receive selpercatinib as of the data cutoff date, TOT will be calculated as follows:

$$\text{TOT (weeks)} = (\text{Last Visit Date} - \text{First Dose Date} + 1)/7$$

6.11.1.2. Dose Intensities

Dose intensities will be summarized descriptively as actual dose intensity (ADI), planned dose intensity (PDI) and relative dose intensity (RDI).

- The actual dose intensity of selpercatinib (mg/day) will be calculated as the actual cumulative dose of selpercatinib (mg) received divided by TOT (days).

- The planned dose intensity of selpercatinib (mg/day) will be as follows:
 - $PDI \text{ (mg/day)} = \text{assigned dose level (mg)} \times 2/\text{day} = 320 \text{ mg/day}$
- The relative dose intensity is the percentage of dose received relative to the planned dose and is defined as follows:

$$RDI (\%) = \left(\frac{ADI}{PDI} \right) * 100\%$$

6.11.1.3. Dosage Modifications

The number and percentage of patients with 1 or more dose reductions, dose omissions, and dose increases will be tabulated with the reason for each dose modification.

6.11.2. Adverse Event

The reported AE term will be coded using the latest version of the Medical Dictionary for Regulatory Activities (MedDRA). AE verbatim text will be mapped by the sponsor or designee to corresponding terminology within MedDRA, and the resulting System Organ Class (SOC) and Preferred Term (PT) will be used for AE summary. The severity of each AE will be graded by the Investigator based on version 5 of the National Cancer Institute (NCI) Common Terminology Criteria for Adverse Events (CTCAE). For AEs without matching terminology within the NCI-CTCAE, Version 5, the investigator will be responsible for selecting the appropriate SOC and assessing severity grade based on the intensity of the event. The causal relationship between the occurrence of an AE and study drug will be judged by the Investigator, and reported by answering yes/no in CRF.

Consolidated AE: Consolidated terms comprising clinically synonymous MedDRA preferred terms have been defined in order to assist in identifying relevant safety differences between treatment arms. Summaries of the incidence of these consolidated terms will supplement the summaries by MedDRA PTs specified in this section. The MedDRA PTs that are grouped under each of the consolidated terms will be provided in compound-level safety document.

A **serious adverse event (SAE)** is any AE during this study that results in one of the following outcomes:

- death
- initial or prolonged inpatient hospitalization (except for study drug administration)
- a life-threatening experience (that is, immediate risk of dying)
- persistent or significant disability/incapacity
- congenital anomaly/birth defect
- considered significant by the investigator for any other reason.

An AE will be regarded as **treatment-emergent**, if

- Its onset date occurs any time on or after the date of first dose up to 28 days after the last dose (or up to any time if serious and considered related to study treatment); or
- It occurs prior to first dose date and worsens while on therapy or up to 28 days after the last

dose of study treatment (or up to any time if serious and considered related to study treatment)

AEs will be summarized based on the number and percentage of patients experiencing events by MedDRA SOC and PT. If a patient experiences repeat episodes of the same AE (as defined by the MedDRA SOC and PT), the patient will only be counted once on the most severe CTCAE grade and the closest relationship to treatment.

The following TEAE/SAE listings and summaries will be provided:

- Overview of AEs
- Summary of TEAE/SAE by PT
- Summary of TEAE/SAE by SOC and PT
- Summary of TEAE/SAE by SOC and PT and maximum CTCAE grade (grades 1~5 and grade ≥ 3)
- Listing of SAE

The summaries above will be repeated for TEAE/SAE related to study treatment.

6.11.2.1. Other Notable Adverse Events

AEs leading to discontinuation of study drug, AEs leading to dose modification, and AEs leading to death will be summarized by SOC and PT (all grades and grade ≥ 3), and by maximum CTCAE grade. Patient-level listings of above AEs will be provided.

6.11.2.2. Adverse Events of Special Interest

Based upon information available to date and/or known class effects of this compound, several categories of AE have been designated to be of special interest. These include the following which are discussed below:

- Hepatic effects/potential liver toxicity (elevated levels of ALT, AST, total bilirubin, direct bilirubin, and ALP)
- Hypersensitivity
- Hypertension
- Thrombocytopenia

Liver function tests will be presented using conventional summary statistics, toxicity shift table analysis, and by time-to-event plots. Possible drug-induced liver injury will be assessed as defined in FDA guidance. Hy's Law cases of drug-induced liver injury have the following components:

- The drug causes hepatocellular injury as evidenced by an elevation of ALT or AST to 3-fold or greater of the upper limit of normal (ULN) relative to control (or in this context to baseline levels)

- In addition to the transaminase increases, an associated (i.e. concomitant) elevation of total serum bilirubin to 2-fold or greater of the ULN without initial findings of cholestasis (elevated alkaline phosphatase)
- No other explanation can be found for the combination of increased transaminase(s) and total bilirubin such as viral hepatitis, pre-existing acute liver disease, or concomitant drug capable of causing the observed injury

Events of hypersensitivity will be identified using search terms that include the preferred terms *Hypersensitivity* and *Drug hypersensitivity* under the *Immune System Disorders* MedDRA system organ class.

Events of hypertension will be identified using the preferred terms *Blood pressure abnormal* and *Blood pressure increased* under the *Investigations* system organ class, as well as the preferred term *Hypertension* under the *Vascular Disorders* system organ class.

Events of thrombocytopenia will be identified using the preferred term *Thrombocytopenia* under the *Blood and lymphatic system disorders* system organ class, as well as the preferred term *Platelet count decreased* under the *Investigations* system organ class.

Additional AEs of special interest may be added based on review of the safety data before the final data extraction.

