 - If previously receiving dose level -2, resume treatment at the same dose level. If a second AE requiring dose modification occurs at dose level -2, discontinue study treatment.
 - For AEs clearly unrelated to study treatment that resolve or return to patient's baseline in ≤14 days, dose reduction is not required.
 - Re-escalation to a prior dose level after a dose reduction is not permitted (other than hypersensitivity, liver test abnormalities, thrombocytopenia, and hypertension).

Permanently discontinue treatment for any of: malignant hypertension, hypertensive crisis, or persistent uncontrolled hypertension despite optimal medical management. Patients with clinical benefit who experience recurrent hypersensitivity reaction or recurrent AST or ALT increase despite dose reductions should be discussed with the CRS/CRP and may be allowed to continue treatment with more than 2 dose reductions if continuation is considered to be safe and in their best interest.

Before the start of each cycle, Grade 3 hematologic toxicity possibly related to selpercatinib must resolve to either baseline or at least Grade 2. If a patient experiences Grade 4 hematologic toxicity possibly related to selpercatinib, then dosing must be suspended (until the toxicity resolves to either baseline or at least Grade 2) and the dose of selpercatinib must be reduced as outlined in [Table 6-1](#).

Before the start of each cycle, nonhematologic toxicity (except AEs with no immediate medical consequence that can be controlled with adequate treatment (e.g. pain, alopecia, neuropathy fatigue, nausea, vomiting, diarrhea, Grade 2 hypothyroidism, or Grade 2 hypertension).) possibly related to selpercatinib must resolve to either baseline or at least Grade 1. If a patient experiences persistent or recurrent Grade 2 nonhematologic toxicity possibly related to selpercatinib that does not resolve with maximal supportive measures within 7 days to either baseline or Grade 1, then dosing may be suspended (until the toxicity resolves to either baseline or at least Grade 1) and the dose of selpercatinib may be reduced as outlined in [Table 6-1](#).

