For patients who experience \geq Grade 3 elevated LFTs at 80 mg BID, the sponsor should be contacted for additional guidance regarding dose modification. If the patient experiences \geq Grade 3 elevated LFTs at a dose of 40 mg BID, selpercatinib should be discontinued. Please refer to Section 8.2.2 for additional monitoring that may need to be initiated.

Dose Modifications for Thrombocytopenia

If a patient is discovered to have thrombocytopenia \geq Grade 3, study drug should be withheld, and the patient should be evaluated for alternative causes (medications/substances, viral studies). A hematology consultation may be considered, as necessary, to understand the etiology and to consider a role for concomitant steroid therapy. The patient should undergo weekly complete blood count (CBC) testing until the event resolves and CBC level returns to normal/baseline. Upon recovery, the patient should resume selpercatinib with a dose reduction of at least 1 level with weekly CBC surveillance for 1 full cycle.

Dose Modifications for Hypertension

Hypertension is defined as:

- a sustained increase in blood pressure from baseline, as evidenced by ≥ 2 readings on ≥ 2 separate occasions, or
- a clinically significant elevation requiring acute treatment.

If hypertension occurs, study drug may be interrupted at the discretion of the investigator while:

- a new antihypertensive medication regimen is initiated, or
- a preexisting regimen is optimized to a reproducible reading of $\leq 140/90$ mmHg.

If study drug is interrupted, it may be resumed at the same or a lower dose at the discretion of the investigator. In all cases, the patient should continue to undergo regular blood pressure monitoring to ensure adequate blood pressure control. Dose re-escalation to the patient's original dose can be considered once adequate blood pressure (BP) control has been obtained; with clinically appropriate monitoring.

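### The hypertension AESI term list in SAP 6.11.2.2 is closed and does not name hypertensive crisis or malignant hypertension, so such events could fall outside the AESI grouping

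*SAP*

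**What the plan says.** SAP 6.11.2.2 designates hypertension an adverse event of special interest. Its rule for finding the events opens with "Events of hypertension will be identified using the preferred terms". Three terms follow: two from the Investigations class (Blood pressure abnormal, Blood pressure increased) and one from the Vascular Disorders class (Hypertension). No wording admits others. The hypersensitivity search in the same section is worded differently: "Events of hypersensitivity will be identified using search terms that include the preferred terms". That list is open; the hypertension list is not.

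Protocol 6.2.4 separates certain events from hypertension in general. For the former: "Permanently discontinue treatment for any of: malignant hypertension, hypertensive crisis, or persistent uncontrolled hypertension despite optimal medical management". For the latter: "If hypertension occurs, study drug may be interrupted at the discretion of the investigator while" blood pressure treatment is started or optimised.

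SAP 6.11.2 sets the level at which adverse events are summarised: "the resulting System Organ Class (SOC) and Preferred Term (PT) will be used for AE summary". It also plans supplementary summaries of consolidated terms made up of clinically synonymous preferred terms, but their content lies elsewhere: "The MedDRA PTs that are grouped under each of the consolidated terms will be provided in compound-level safety document".

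**The concern.** An AESI grouping is meant to gather all reported forms of a known risk in one place. Here the protocol attaches its strictest hypertension rule to events that the SAP's search does not name. A programmer who follows SAP 6.11.2.2 literally would select three preferred terms. An event coded as hypertensive crisis or malignant hypertension would not be among them. The AESI output could then show less than the discontinuation table shows for the same risk, and a reader would have to reconcile the two by hand.

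The stake is the completeness of a descriptive safety grouping. Detection of events, patient management and the efficacy endpoints are not affected.

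**Working it through.** The SAP gives no expected count for this AESI, so there is no planned figure for the grouping itself to reproduce. The check is a comparison of texts followed by a small calculation.

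**Step 1: compare the lists.**

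| Named in protocol 6.2.4 for permanent discontinuation | On the SAP 6.11.2.2 list? |
|---|---|
| Malignant hypertension | No |
| Hypertensive crisis | No |
| Persistent uncontrolled hypertension | Not by that name; it describes the course of hypertension, so the listed term Hypertension may cover it. The documents do not settle this. |

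None of the three SAP terms names either of the first two diagnoses.

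**Step 2: follow an event through coding.** Protocol 8.2.3 has the investigator supply the verbatim term and the sponsor or its designee map it to MedDRA. Protocol Appendix H tells sites to report a related diagnosis in place of an abnormal test value, and uses raised blood pressure and hypertension as an example. A site seeing a crisis is therefore steered towards naming it, so the two Investigations terms are not a dependable fallback. Because SAP 6.11.2 works at preferred-term level, an event coded outside the three terms is outside the grouping.

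**Step 3: look for wording that would bring these events back in.** Two places come close.
- The consolidated terms only supplement the preferred-term summaries. SAP 6.11.2.2 does not refer to them, and the SAP does not show which terms they contain.
- The closing sentence of SAP 6.11.2.2 allows further AESIs to be added after review of safety data. It does not commit to widening the list for an existing one.

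**Step 4: size.** Inputs: n = 75 (protocol 9.3, SAP 5.2). The documents give no rate for crisis or malignant hypertension, so the true rate p for the two combined is an assumption, shown as a range.

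Formulas: expected events = 75p (at most one per patient); chance of at least one = 1 − (1 − p)^75.

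The formula is first checked against the plan's own statement of approximately 80% and 98% for true rates of 2% and 5%:
- p = 0.02: 1 − 0.98^75 = 78.0%
- p = 0.05: 1 − 0.95^75 = 97.9%

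Both agree with the stated figures to within about 2 points. Then, for the assumed rates:

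| Assumed p | Expected events (75p) | Chance of at least one |
|---|---|---|
| 0.5% | 0.375, about 0.4 | 1 − 0.995^75 = 31% |
| 1% | 0.75 | 1 − 0.99^75 = 53% |
| 2% | 1.5 | 1 − 0.98^75 = 78% |

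One patient is 1/75 = 1.3 percentage points. A patient who also has an event coded Hypertension remains in a per-patient count. In that case the proportion does not change, and only the severe event and its grade are missing from the grouping.

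**The case against.** The strongest reply has four parts.

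- **Coding.** That these events fall outside the three terms is a statement about the MedDRA hierarchy, which neither document reproduces. The protocol shows only that it names them separately. This stands, and the point has to be conditional on separate coding.
- **Visibility.** SAP 6.11.2 tabulates all TEAEs and SAEs by preferred term and by maximum grade, and lists SAEs. SAP 6.11.2.1 tabulates and lists events that led to stopping study drug, and under protocol 6.2.4 these events should be among them. SAP 6.11.5 adds blood pressure summaries and a listing. This also stands: no event disappears from safety reporting.
- **Unspecified output.** SAP 6.11.2.2 says how hypertension events are identified but describes no hypertension AESI table. That is true, but an identification rule has no purpose unless some output uses it, and any such output would inherit the gap.
- **Ranking.** The protocol does not call these events the most serious. It attaches permanent discontinuation to them and to persistent uncontrolled hypertension alike. This stands as a limit on wording; that rule is reason enough to expect them in the grouping.

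A reader might also infer a much larger shortfall from protocol 1.5, which reports hypertension in 36.3% of patients at any grade and 19.0% at Grade 3-4 in the earlier study. Applied to 75 patients these give about 27 (0.363 × 75) and 14 (0.190 × 75). The documents do not support that use. Those rates are reported for hypertension, a term the search does contain, so they count events it would find. Protocol 1.5 names neither crisis nor malignant hypertension among the Grade 3-4 events it lists, and puts each unlisted one below 2% of patients. If they were reported there as separate Grade 3-4 terms, each would be expected in fewer than 0.02 × 75 = 1.5 patients here.

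**Conclusion.** The point holds as a limited gap in the AESI definition. The list is closed, it omits two diagnoses that protocol 6.2.4 singles out, and nothing else in the SAP commits to including them. If coded to their own preferred terms, they would be left out of the hypertension AESI grouping.

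The likely size is zero to a few events: about 0.4 to 1.5 expected over assumed rates of 0.5% to 2%. This rests on three assumptions: separate coding, those rates, and 75 treated patients.

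It would go too far to conclude that the AESI count will certainly miss such events, or that its frequency and grade will be understated. Either requires that an event occurs and is coded outside the list. A lower patient count further requires that the patient has no other qualifying event.

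**What to change.** In SAP 6.11.2.2, add Hypertensive crisis and Malignant hypertension to the hypertension term list. Alternatively, define the AESI by the compound-level consolidated hypertension term, after checking that it contains both and citing the document and version. Apply the same grouping to every hypertension AESI output.

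The cost is one line of SAP wording and a matching change to the term selection in the programs. No new data are needed and no clinical rule changes.
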